### 6.3.14.3 Reporting Adverse Events

All AEs reported or observed after the patient signs the ICF until Day 28 visit will be recorded on the AE page of the eCRF. Information to be collected includes event term, time of onset, investigator-specified assessment of severity and relationship to study drug, date of resolution of the event, seriousness, any required treatment or evaluations, and outcome. Adverse events resulting from concurrent illnesses, reactions to concurrent illnesses, reactions to concurrent medications, or progression of disease states must also be reported. All AEs will be followed to adequate resolution. The Medical Dictionary for Regulatory Activities (MedDRA) will be used to code all AEs.

Any AE that meets SAE criteria (see Section 6.3.14.1) must be reported to the PPD Pharmacovigilance Department immediately (i.e., within 24 hours) after the time site staff first learn about the event. The following contact information is to be used for SAE reporting:

### 6.3.14.4 Assessment of Severity

The severity of an AE refers to the extent to which an AE affects the patient's daily activities. The severity of the AE will be rated as mild, moderate, or severe using the following criteria:

Mild:	These events require minimal or no treatment and do not interfere with the patient's daily activities.
Moderate:	These events are sufficiently discomfoting to interfere with normal activities.
Severe:	These events interrupt a patient's usual daily activity and may require systemic drug therapy or other treatment. Severe events are usually incapacitating.

When changes in the severity of an AE occur more frequently than once a day, the maximum severity for the event should be noted for that day. Any change in severity of signs and symptoms over a number of days will be captured by recording a new AE, with the amended severity grade and the date (and time, if known) of the change. Changes in the severity of an AE should be documented to allow an assessment of the duration of the event at each level of intensity to be performed.

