#### **6.3.14.2 Eliciting and Documenting Adverse Events**

Adverse events will be collected and assessed from the time the patient signs the ICF until Day 28 visit for all AEs (including SAEs) regardless of its relationship to study drug. Any AE that occurs during or after the first dose of study drug is considered treatment emergent.

At every study visit, patients will be asked a standard non-leading question to elicit any medically related changes in their well-being. At follow-up visits, they will also be asked if they have been admitted to the hospital, had any accidents, used any new medications, or changed concomitant medication regimens.

When patients have left the hospital they will be instructed to contact the investigator at any time if any symptoms develop.

Adverse events and SAEs that occur after Day 28 visit, will be reported to PPD or sponsor, only if the investigator considers them possibly, probably, or definitely related to study drug.

In addition to patient accounts, AEs will be identified through physical examination, review of laboratory values, diagnostic test findings (Section 6.5) and monitoring in the ICU/healthcare facility and (if relevant) report from carers..

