9.1.1. Incidence of Adverse Events

Summaries of the total number of TEAEs and the number and percentage of patients with at least one TEAE will be provided by treatment group. Treatment emergent AEs will be presented by SOC and PT. At each level of patient summarization, a patient is counted once if the patient reported one or more events.

All AEs will be presented in a listing.

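### Protocol 6.3.14.4 opens a new AE at each day-to-day change in severity and SAP 9.1.1 does not link those records, so the total number of TEAEs can mix distinct events with severity steps

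*Protocol*

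**What the plan says.** Protocol 6.3.14.4 sets two recording rules.

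- When severity changes more than once within a day, "the maximum severity for the event should be noted for that day".
- Across days the rule differs: a change of severity in either direction "will be captured by recording a new AE, with the amended severity grade and the date (and time, if known) of the change". The direction of the change is not restricted.

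The stated purpose is to "allow an assessment of the duration of the event at each level of intensity to be performed". The protocol thus treats the several records as parts of one event.

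SAP 9.1.1 plans the following output: "Summaries of the total number of TEAEs and the number and percentage of patients with at least one TEAE will be provided by treatment group". Its only rule against double counting works per patient: "a patient is counted once if the patient reported one or more events". SAP 9.1.2 counts a patient once at the most related event, and SAP 9.1.3 once at the most severe. SAP 9.1.4 and 9.1.5 follow the pattern of 9.1.1. None of these sections says how records of one event are joined.

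On treatment emergence, Protocol 6.3.14.1 and SAP 9.1 require an event to be absent before exposure, or to get worse in intensity or frequency once dosing has begun. Protocol 6.3.14.2 collects AEs from consent and uses timing alone: "Any AE that occurs during or after the first dose of study drug is considered treatment emergent".

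**The concern.** The recording rule serves duration by severity grade. The SAP then puts a count on top of those records without defining its unit. A programmer who follows both texts literally has no instruction to rejoin the pieces, so one event that fluctuates can enter the total several times. The arm totals would then depend partly on how often severity changes from day to day and not only on how many events occurred. Protocol 6.3.14.3 requires events from concurrent illness and disease progression to be reported, so changes of grade are plausible in this ICU population.

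The second issue concerns which records qualify. A post-dose record that exists only because a pre-dose event improved passes the timing rule and fails the definition. Here a patient-level count could move as well as the total.

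**Working it through.** The documents state no TEAE count, so there is no figure to reproduce. The check is a counting identity plus a comparison of texts.

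**Records per event.** Input: the across-days rule in Protocol 6.3.14.4. An event starts with one record, and each day-to-day change adds one. With k such changes, records = k + 1. Changes within a day do not add to k, because only that day's maximum is kept.

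**Illustration (assumed course).** One post-dose event goes mild, moderate, severe, moderate, mild on separate days, so k = 4.

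| Counting unit | Contribution to the total |
|---|---|
| Each record as created | 4 + 1 = 5 |
| First record plus worsening steps only | 1 + 2 = 3 |
| Linked episode | 1 |

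The patient-level count is 1 in every row, and the SAP 9.1.3 table shows the patient as severe in every row.

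**Total per arm.** With N distinct events and a mean of m day-to-day changes per event, the record count is N × (1 + m). The documents give no value for m, so the values below are assumptions:

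- m = 0.25: 1 + 0.25 = 1.25 times the number of events
- m = 1: 1 + 1 = 2.0 times
- m = 2: 1 + 2 = 3.0 times

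An event whose grade stays constant has k = 0 and counts once, so the multiplier is 1 when no event changes grade.

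**Events that begin before the first dose.** Take an AE that starts after consent and before dosing, and compare the two rules on the record opened by a change after dosing.

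| Change after dosing | Timing rule (Protocol 6.3.14.2) | Definition (Protocol 6.3.14.1, SAP 9.1) |
|---|---|---|
| Worsens | TEAE | TEAE |
| Improves | TEAE | Not a TEAE |

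The rules part only in the second row. If the patient has no other TEAE, the count of patients with at least one TEAE differs by one between the two rules. The same applies to a preferred-term row if the patient has no other qualifying record of that term.

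**The case against.** The best defence is that the SAP nowhere says it counts eCRF records. It speaks of TEAEs and defines a TEAE as an event, under which an improvement step is neither new nor worse. That stands: the defect is an undefined unit with no linking rule, not an instruction to count records. A reader might infer that the total counts severity steps instead of events. The documents do not support that, because constant-grade events count once, changes within a day reduce to one grade, and the unit is left open.

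A reader might also take the total for a headline safety figure. Protocol 7.7.3 plans only patient-level TEAE counts, no test, dose-selection criterion or stopping rule uses the total, and all AEs are listed, so split records would be visible. This keeps the point minor. It does not define the reported figure.

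A claim that the arm with longer survival or ICU stay would be disadvantaged goes too far. Any raw AE count rises with observation time, and a count of linked episodes would too.

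On the pre-dose conflict, the SAP adopts the stricter definition and does not repeat the timing sentence. The window is also short: Protocol 6.2.2 fits screening and baseline within 24 hours of the SA-AKI diagnosis, and Protocol 6.3.14.1 does not report a condition present at screening unless it deteriorates. The conflict is narrow, but the two protocol sections still disagree.

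Lastly, the eCRF layout and table shells are not in the documents, so records may already carry a link. If so, the SAP need only say that it is used.

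**Conclusion.** The point holds as a minor one. Followed as written, the recording rule lets an event with k day-to-day changes of severity add up to k + 1 to the TEAE total, and the SAP has no step that prevents it. The size of the effect is unknown; the multipliers of 1.25 to 3 rest on assumed rates of change. Whether the arms would be affected unequally cannot be judged from the documents.

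Patient-level incidence, by system organ class and preferred term, by severity and by relationship, is not affected by the extra records. The one exception is the AE that begins between consent and first dose and then improves. Its effect on patient counts depends on the timing rule being applied instead of the SAP's own definition.

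**What to change.** In SAP 9.1.1, define the unit of the total. Link records of the same patient and preferred term when the next one starts as the previous one stops because of a change in grade. Count each linked episode once, at its maximum severity, and keep the separate records in the listing so that duration by grade can still be assessed.

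Flag an episode as treatment emergent only if it first starts, or worsens in intensity or frequency, after the first dose. Reconcile Protocol 6.3.14.2 with Protocol 6.3.14.1 and SAP 9.1 so that one rule applies.

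The cost is SAP wording, a clarification in the protocol and one extra derivation. Term, onset, grade and resolution date are already collected under Protocol 6.3.14.3. The downside is a small risk of merging two distinct events with the same term that happen to follow one another directly; linking by preferred term alone, without the condition on dates and grade change, would make that risk larger. If no linking is wanted, the minimum is to label the total as a number of AE records.

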### **6.3.14.5 Assessment of Causality**

The assessment of the relationship of an AE to the administration of study drug (unrelated, possible, probable, definite) is a clinical decision based on all available information at the time of completion of the eCRF. As per the International Council for Harmonisation harmonised tripartite guideline E6(R1): Good Clinical Practice (ICH E6[R1]) guidelines, factors to be considered include the following:

- Temporal sequence from drug administration: the event must occur after the study drug is given. The length of time from exposure to medication to event should be evaluated in the clinical context of the event.
- Recovery on discontinuation (dechallenge) and recurrence on reintroduction (rechallenge).
- Underlying, concomitant, intercurrent diseases: each report should be evaluated in the context of the natural history and course of the disease being treated and any other disease the patient may have had prior to, or developed during the course of the study.
- Concomitant medication or treatment: the other drugs the patient is taking or the treatment the patient is receiving at the time of the event should be examined to determine whether any of them may be recognized to cause the event in question.
- The pharmacology and PK of the study drug: absorption, distribution, metabolism, and excretion of the study drug or other medications the patient is receiving coupled with the PD responses should be considered when evaluating an event.

The investigator's assessment of an AE's relationship to study drug is part of the documentation process. If there is any doubt as to whether a clinical observation is an AE or whether it is related to study drug, the event should be reported.

The relationship or association of the study drug in causing or contributing to the AE will be characterized using the following classification and criteria:

- Unrelated: This relationship suggests that there is no association between the study drug and the reported event.
- Possible: This relationship suggests that treatment with the study drug caused or contributed to the AE; i.e., the event follows a reasonable temporal sequence from the time of drug administration or follows a known response pattern to the study drug, but could also have been produced by other factors.
- Probable: This relationship suggests that a reasonable temporal sequence of the event with drug administration exists and, based upon the known pharmacological action of the drug, known or previously reported adverse reactions to the drug or class of drugs, or judgment based on the investigator's clinical experience, the association of the event with the study drug seems likely. The event disappears or decreases on cessation or reduction of the dose of study drug.
- Definite: This relationship suggests that a definite causal relationship exists between drug administration and the AE, and other conditions (concurrent illness, progression/expression of disease state, or concurrent medication reaction) do not appear to explain the event. The event reappears or worsens if the study drug is re-administered.

#### **6.3.14.6 Follow-up of Patients Reporting Adverse Events**

All AEs must be reported in detail on the appropriate page of the eCRF and followed to satisfactory resolution, until the investigator deems the event to be chronic or not clinically significant, until the patient is considered to be stable or subject is lost to follow-up.

### **6.4 Pregnancy**

The effect of recAP on pregnancies or infants is not known, as the safety of this drug during pregnancy has not been tested previously in either human or in animal studies. Because AP is present in the human placenta it is theoretically possible that anti-placental antibodies are developed after receiving study drug. Such antibodies could interfere with the ability to have a successful pregnancy. While development of anti-drug antibodies has not been seen to date in human studies, the safety experience with this drug is limited to only 37 subjects who received study drug and no data are available regarding effect of the drug on human reproduction.

Therefore, female patients who are pregnant or lactating/breastfeeding at time of screening or who intend to become pregnant within 28 days of enrolling into the study will be excluded from the study (see Section 4.1.2). If a pregnancy occurs while a patient is participating in the study, it is not regarded as an AE unless there is a suspicion that an investigational product may have interfered with the effectiveness of a contraceptive medication. Any pregnancy that occurs during study participation must be reported using a clinical study pregnancy form. To ensure patient safety, each pregnancy must be reported to AM-Pharma B.V. within 2 weeks of learning of its occurrence. The pregnancy must be followed-up to determine outcome (including spontaneous miscarriage, elective termination, normal birth, or congenital abnormality) and status of mother and child, even if the patient was discontinued from the study. Pregnancy complications and elective terminations for medical reasons should not be reported as an AE or SAE. Spontaneous miscarriages must be reported as SAEs.

Any SAE occurring in association with a pregnancy, brought to the investigator's attention after the patient has completed the study, and considered by the investigator as possibly related to the study drug, must be promptly reported to AM-Pharma B.V.

## **6.5 Laboratory Analyses**

Any abnormal laboratory test results (hematology, clinical chemistry, or urinalysis) or other safety assessments (e.g., ECGs, vital sign measurements), including those that worsen from baseline, felt to be clinically significant in the medical and scientific judgment of the investigator, are to be recorded as (S)AEs.

## **7 Statistical and Analytical Plan**

### **7.1 Primary Endpoint**

The primary endpoint will be calculated from time-corrected endogenous creatinine clearance measurements on Day 1 (first measurement after treatment) to Day 7, inclusive. Time-corrected endogenous creatinine clearance is assessed on each day during a  $6 \pm 1$  hour period and calculated in mL/min as the mean creatinine clearance over the period, which is expected to be representative of the full 24 hours for that day. The primary endpoint is the area under the time-corrected endogenous creatinine clearance curve from Day 1 to Day 7 ( $AUC_{1-7}$ ), calculated as the average of the time-corrected endogenous creatinine clearance

values over the 7 days. Specifically, denoting  $C_i$  as the mean time-corrected endogenous creatinine clearance on Day  $i$ ,  $AUC_{1-7}$  is defined as:

$$AUC_{1-7} = \frac{1}{7} \sum_{i=1}^7 C_i$$

Any missing  $C_i$  values will be handled by linear interpolation where possible, otherwise they will be imputed by last observation carried forward (LOCF). When there are no preceding post-baseline measurements to use, the baseline measurement (i.e., prior to treatment) will be carried forward.

## 7.2 Key Secondary Endpoint

The key secondary endpoint is RRT incidence during the period Day 1 (after first treatment) to Day 28, inclusive. Should a patient die or withdraw from the study during this period without recording RRT incidence, he or she will be counted as having not required RRT. The analysis of this endpoint will be repeated excluding patients who died or withdrew from the study prior to completion of this period.

## 7.3 Other Secondary Endpoints

### 7.3.1 Renal

- Renal endpoints include the following:
- Volume of urine (daily from Day 1 to Day 7, inclusive, and on subsequent visit days if reliable urine collection is possible)
- Serum creatinine and BUN (daily from Day 1 to Day 7, inclusive, and on subsequent visit days if reliable urine collection is possible)
- BUN clearance (daily from Day 1 to Day 7, inclusive, and on subsequent visit days if reliable urine collection is possible)
- Peak value of serum creatinine and BUN (during the period Day 1 to Day 7, inclusive)
- RRT-free days (during the period Day 1 to Day 28 excluding patients who died or withdrew from the study prior to the end of this period), i.e., 28 days minus the number of days a patient is on RRT during this period. An RRT-free day is defined as a day on

which a patient did not receive any form of RRT. Conversely, a day on RRT is defined as a day on which a patient received any form of RRT for any period of time on that day.

For intermittent RRT, the following additional rules apply:

- a. Following conclusion of intermittent RRT, if the patient then has a period of six or more days before next initiation of any form of RRT, all (six or more) days in this intervening period are counted as RRT-free
  - b. Following conclusion of intermittent RRT, if the patient then has a period of five or less days before next initiation of any form of RRT, all (five or less) days in this intervening period are counted as on RRT
- Total number of days on RRT (during the period Day 1 to Day 28, inclusive). A day on RRT is defined as a day on which a patient did receive any form of RRT for any period of time on that day.
  - Reasons for initiation of RRT (during the period Day 1 to Day 28, inclusive)
  - Kidney function at Day 28 as assessed by measured creatinine clearance if available, otherwise as assessed by eGFR (estimated by the CKD-EPI formula based on serum creatinine). Patients who die prior to Day 28 will be excluded from this endpoint, with any other missing assessments (including early withdrawals) imputed using LOCF.
  - Kidney function at Day 60 and Day 90 as assessed by eGFR (estimated by the CKD-EPI formula based on serum creatinine). Patients who die prior to Day 60 or Day 90, respectively, will be excluded from this endpoint, with any other missing assessments (including early withdrawals) imputed using LOCF.
  - Sustained loss of kidney function at Day 60 and Day 90, defined by  $eGFR < 60$  mL/min (with eGFR estimated by the CKD-EPI formula based on serum creatinine). Patients who die prior to Day 60 or Day 90, respectively, will be excluded from this endpoint, with any other missing assessments (including early withdrawals) at Day 60 or Day 90 imputed using LOCF.
  - Incidence of dialysis dependency at Day 60 and Day 90. Patients who die or withdraw from the study prior to Day 60 or Day 90, respectively, without recording incidence of dialysis dependency will be counted as not having required dialysis dependency.

### 7.3.2 Other Organs

Endpoints for organs other than renal function include the following:

- Liver enzymes (AST, ALT, GGT, LDH, bilirubin but excluding AP).
- Lung function as assessed by arterial PaO2, FiO2, P/F ratio, PEEP, and tidal volume in mechanically ventilated patients.
- Ventilator-free days (from Day 1 to Day 28, inclusive), i.e., 28 days minus the number of days a patient is on ventilator during this period. Should a patient die or withdraw prior to Day 28, the days remaining in this period will be counted as per the status of the patient at time of death or withdrawal.
- Time from start of first administration of study drug to being off-ventilator (from Day 1 to Day 28, inclusive) for those patients who are on ventilator at the start of this period. Patients who remain on ventilator will be censored at the earliest of Day 28 or withdrawal from the study for any reason.
- Shock-free days (during the period Day 1 to Day 28, inclusive), i.e., 28 days minus the number of days a patient is on inotropic or vasopressor therapy during this period. Should a patient die or withdraw prior to Day 28, the days remaining in this period will be counted as per the status of the patient at time of death or withdrawal. A patient is considered to be shock free if he or she is not on vasopressors or inotropic agents (including but not limited to noradrenaline, adrenaline, dobutamine, dopamine, vasopressin, and enoximone).
- Time from start of first administration of treatment to being shock free (from Day 1 to Day 28, inclusive) for those patients who are not shock free at the start of this period. Patients who do not become shock free will be censored at the earliest of Day 28 or withdrawal from the study for any reason.
- SOFA scores during ICU or intermediate care unit stay.
- Number of dysfunctional organs as assessed by SOFA scores.
- Deaths during the 90-day study period (by recording date).

